POB/ /
Berlaku mulai:

15 Mei 2015

http://www.pjnhk.go.id/

Study Protocol

Hal 1 dari 6

LAMPIRAN 3 FL/03-010/01.0

Study Protocol Summary

Title

Low Dose Continuous Furosemide Effect on Cardiac Surgery Patients With Kidney Dysfunction

Main Researcher

dr. [name], SpAn., M.Kes., KAKV

RS Jantung dan Pembuluh Darah Harapan Kita, Jakarta

Sponsor

none

Aims

- to Analyze trends in estimated glomerular filtration rate parameters from administration of low-dose furosemide continuous infusion in patients with mild-moderate renal dysfunction undergoing cardiac surgery.
- 2. 2. To analyze the need for a therapeutic dose of intravenous diuretic after low-dose continuous furosemide in patients with mild to moderate renal dysfunction undergoing cardiac surgery.
- 3. To analyze the need to use renal replacement therapy as a marker of worsening renal function leading to acute renal failure after continuous administration of low-dose furosemide in patients with renal dysfunction undergoing cardiac surgery.

Ethical Issue(s) of the Protocol

- 1. Administration of fluids or drugs to patients that can affect patient outcomes
- 2. Taking blood samples from patients for laboratory examination
- 3. Evaluating the effects of drug administration
- 4. Patient condition follow up in study period
- 5. Inconvenience of patient or family for additional information needed in research involvement

POB/ /
Berlaku mulai:

15 Mei 2015

Hal 2 dari 6

LAMPIRAN 3 FL/03-010/01.0

http://www.pjnhk.go.id/

Study Protocol

Study Design

Clinical Study: double blinded randomized controlled study

Anticipated Outcome

Perioperative administration of low dose continuous furosemide infusion can gives protective effect in cardiac surgery patients with mild to moderate kidney, Measured by the improvement of post operative eGFR

Inclusion and exclusion criteria

Inclusion criteria:

- 1) 18-65 years old
- 2) Undergo elective heart surgery, types of surgery: coronary bypass (coronary artery bypass graft/CABG), single heart valve replacement surgery, one or two heart valve repair surgery, coronary bypass surgery with single heart valve repair/replacement.
- 3) Using cardiopulmonary bypass machine in surgical procedures
- 4) Patients with ejection fraction >40%
- 5) Patients with mild to moderate impaired renal function (eGFR 30-89 mL/min/1.73 m2 and have never had renal replacement therapy

Exclusion criteria:

- 1) Heart disease patients with ejection fraction < 40%

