Ethical clearance for the study was approved by Institutional Review Board of National Cardiovascular Center Harapan Kita. Patients eligible for the study was recruited and written informed consent was obtained after clear explanation of the study. Allocation of furosemide and control group was done using simple computer randomization by staff who was not involved in the study. Furosemide infusion and normal saline was prepared by independent pharmacist blinded to the study. Furosemide solution was prepared to contain 40 mg of furosemide diluted with normal saline to a total volume of 40 cc (1 mg / 1 cc) and control solution was prepared to contain only 40 cc of normal saline. Both solution was packaged in 50-cc syringe and prepared in similar fashion. The solution was administered after induction of anesthesia with rate of 2 cc

Study Protocol

POB/ /
Berlaku mulai:

15 Mei 2015

Hal **4** dari **6**

LAMPIRAN 3 FL/03-010/01.0

http://www.pjnhk.go.id/

per hour for 12 hours.

Metode Analisa*

The data obtained will be analyzed using the SPSS software program. Basic characteristic data will be displayed according to the specified variable type. Numerical variables with normal distribution will be displayed in the form of mean ± standard deviation or median (minimum-maximum) if the distribution is not normal. Categorical variables will be displayed as a percentage (amount). Data from the two groups were analyzed using x2 analysis (chi square) or Fisher's exact test, respectively. The level of statistical significance refers to the P value <0.05

Evaluation Criteria (Response/Outcome)

changes in glomerular filtration rate parameters after intervention in subjects will be evaluated, the need/indication for therapeutic diuretic therapy, and use of renal replacement therapy, length of stay in the ICU and incidence of mortality will be analyzed.

Safety Parameters Criteria (Toxicity)

Renal Function pre and post treatment

Blood gas analysis

Blood electrolyte

POB/ /
Berlaku mulai:

15 Mei 2015

Study Protocol Hal 5 dari 6

LAMPIRAN 3 FL/03-010/01.0

http://www.pjnhk.go.id/

Abstract

[figure not shown]
Background:

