The study design was a double-blind randomized controlled trial. Subjects will be randomly divided into 2 groups; the furosemide group (n=43) and the control group (n=44). This study started since May 28, 2021; after obtaining an ethical clearance from the hospital ethics committee. Inclusion criteria included patients aged 18-65 years with left heart ejection fraction >40%, mild to moderate renal dysfunction category (eGFR 30-89 mL/min/1.73 m2) who underwent elective cardiac surgery; such as coronary artery bypass graft (CABG), replacement of one heart valve, repair of one or two heart valves, and using cardiopulmonary bypass machine. Exclusion criteria included heart disease patients with stage 4-5 chronic renal failure, on renal replacement therapy, cardiac ejection fraction <40%, emergency or repeat surgery, complex heart disease, congenital heart disease, aortic vascular surgery, massive bleeding, sepsis, and currently participating in other research. Continuous furosemide (2 mg/hour) or 0.9% NaCl (2 mL/hour) was given after the induction of anesthesia and continued until 12 hours of administration. After drug administration was completed (12 hours) the first blood sample was obtained to check blood urea nitrogen concentration, urea, creatinine serum and estimated glomerular filtration rate. Sampling was repeated again at the 24th hour, 48th hour and 120th hour since the drug was started. A decrease in GFR > 20% of the preoperative value is considered a decrease in renal function, and an increase of >20% of third sample value in the fourth sample is considered an improvement of renal function. Deterioration of renal function to severe renal dysfunction or requiring renal replacement therapy is considered an event of acute renal failure.

Keywords: Furosemide, Glomerulus Filtration Rate, Renal Dysfunction, Cardiac Surgery

Researcher,

dr. [name], SpAn, M.Kes, KAKV

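### The plan names only chi-square and Fisher's exact for comparing the arms, so the eGFR trend (first-listed aim) and ICU stay have no fitting between-arm test

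*Combined protocol and SAP*

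**What the plan says.** The first entry under Aims is to "Analyze trends in estimated glomerular filtration rate parameters from administration of low-dose furosemide continuous infusion". Evaluation Criteria says that "changes in glomerular filtration rate parameters after intervention in subjects will be evaluated", adds diuretic need and renal replacement therapy (RRT), and ends with "length of stay in the ICU and incidence of mortality will be analyzed".

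The Abstract (Methods) takes a first sample when the infusion ends at 12 h, and then: "Sampling was repeated again at the 24th hour, 48th hour and 120th hour since the drug was started". It turns eGFR into categories by two rules. The rule for worsening uses the value before surgery as its reference: "A decrease in GFR > 20% of the preoperative value is considered a decrease in renal function". The rule for recovery uses only the last two samples: "an increase of >20% of third sample value in the fourth sample is considered an improvement of renal function". It also defines acute renal failure as reaching severe dysfunction or needing RRT. The groups are 43 (furosemide) and 44 (control).

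Metode Analisa describes how numerical data are shown ("Numerical variables with normal distribution will be displayed in the form of mean" with SD, or else as a median with range). On comparing the arms it has one sentence: "Data from the two groups were analyzed using x2 analysis (chi square) or Fisher's exact test, respectively". Significance is P below 0.05; sidedness is not stated. No primary endpoint is labelled.

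**The concern.** Chi-square and Fisher's exact compare proportions. A trend in a numerical measurement over four samples, or a duration, cannot be tested by them unless it is first cut into categories. Two things are at stake. The first-listed aim and ICU stay would go untested between the arms, or the test would be picked once the data are visible, with a free choice of sample, of change or level, and of model. And the categories that do have a test do not answer the first aim: one of them is not measured against the preoperative value at all.

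**Working it through.** **Step 1. Match each outcome to the tests named.**

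| Outcome | Where stated | Type | Fitting test named? |
|---|---|---|---|
| eGFR trend or change, 12/24/48/120 h | Aims; Evaluation Criteria; Abstract | numerical, repeated | no |
| ICU stay | Evaluation Criteria | duration | no |
| Decrease >20% from preoperative value | Abstract | yes/no | yes, but the sample at which it is judged is not stated |
| Rise >20% from third to fourth sample | Abstract | yes/no | yes |
| Acute renal failure | Abstract | yes/no | yes |
| Diuretic need, RRT, mortality | Aims; Evaluation Criteria | yes/no | yes |

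The plan gives no sample-size derivation or other figure to reproduce on this point.

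**Step 2. What the improvement rule measures.** A patient is improved if (120 h value / 48 h value) − 1 > 0.20.

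- Preoperative 60, 48 h 36, 120 h 44: 44/36 − 1 = +22%, so improved. Against the preoperative value, 44/60 − 1 = −27%.
- A patient held at 60 throughout: 60/60 − 1 = 0%, so not improved.

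**Step 3. Which way the two 20% rules point.** The inputs are assumptions, apart from the group sizes of 43 and 44. eGFR falls to 65% of the preoperative value at 48 h in 12% of treated and 35% of control patients (or 15% and 40%). The rest are unchanged, and there is no measurement noise.

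- Decrease rule at 48 h: 0.65 − 1 = −35%, so every fall counts.
- Improvement rule: the 120 h value must exceed 1.20 × 65% = 78% of the preoperative value. Recovery to 85% gives 85/65 − 1 = +31%, so every fall counts as improved. Recovery to 75% gives 75/65 − 1 = +15%, so none does.

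With recovery to 85%, both rules therefore produce the same two-by-two table, with opposite meanings. The test is z = (p1 − p2) / √[p(1 − p)(1/43 + 1/44)], significant if |z| > 1.96. Summing exact binomial probabilities over all tables gives significance in 74% of trials (12% v 35%) and 77% (15% v 40%). This favours the drug under the decrease rule and control under the improvement rule.

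Simulations with patient-level SD of 5–20% of the preoperative value gave:

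| Case | Significant for control, improvement rule, all patients counted |
|---|---|
| Falls recover to 85–95% by 120 h | 19–77% |
| Falls recover to 75% | 7–29% |
| Falls persist at 65% | 0–6% |

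In the 85–95% recovery case the decrease rule at 48 h was significant for the drug in 28–77% of trials. If improvement is counted only among patients with a >20% fall at 48 h, significance for control drops to 0–27%.

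**Step 4. Would a continuous analysis have more power?** Simulations assumed 43 v 44 patients and preoperative eGFR of mean 65 and SD 14, truncated to 30–89. They compared the arm difference averaged over the four samples with chi-square on the >20% decrease at 48 h.

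| Assumed effect | Averaged contrast | Chi-square at 48 h |
|---|---|---|
| Uniform shift of 8 mL/min/1.73 m² at all four samples | 68–95% | 44–56% |
| Large falls prevented in a subset | 21–71% | 30–78% |

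The ranking depends on the form of the effect, which the documents do not give.

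**The case against.** The document is headed a summary. Its comparison sentence ends in a word that promises paired terms and has none, so text may have been lost, and it may have been meant for categorical data alone. That is plausible. A reader might infer that the investigators chose to apply chi-square to continuous eGFR; the wording does not support so much. But if the sentence is limited to categorical data, the eGFR trend and ICU stay have no test at all, so the gap remains on either reading.

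A stronger objection is that Anticipated Outcome judges benefit by better eGFR after surgery, and the Abstract defines improvement as a yes/no rise. On that reading the measure of success is binary and chi-square suits it. Trends could also mean description only. This stands in part: no primary endpoint is labelled, so the first-listed aim cannot be called primary. It does not close the gap, because a randomised comparison that lists GFR change and ICU stay as outcomes needs a test for each, and the improvement rule uses only the third and fourth samples.

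Three further inferences are tempting and go too far.

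- That eGFR is compared only through the 20% cut-offs: the severe-dysfunction part of acute renal failure is a third eGFR category.
- That the improvement rule makes a protective drug look worse: this needs falls that largely recover by 120 h and a count over all patients. The document gives no denominator, and the decrease rule points the other way.
- That a continuous analysis is more powerful: in the subset scenarios it was generally weaker.

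**Conclusion.** The point holds as an omission, with high confidence, and must be fixed: the plan contains no between-arm test that can compare the eGFR trend or ICU stay. This rests on the text alone and needs no assumption. Its consequence is that inference on eGFR is confined to yes/no categories or left to a choice made after the data are seen. The weakness of the improvement rule as a substitute is arithmetic. How often that rule would favour control is conditional on assumed event rates, recovery and noise, and ranges from close to none when falls persist to about three trials in four when they nearly resolve. No claim is made that the present tests are wrong for the binary endpoints, or that the change raises power.

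**What to change.** In Metode Analisa:

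- **eGFR.** Compare the arms with a linear mixed model of the 12, 24, 48 and 120 h values, with arm, time, arm-by-time and preoperative eGFR as a covariate. Name one contrast in advance as the main one (for example the arm difference averaged over the four samples), with its sidedness and a 95% CI. Report the differences at each time as secondary.
- **Patients included.** Use all measured values of all randomised patients, including any measured after a withdrawal criterion is met, and state how values after RRT or death are treated.
- **ICU stay.** Use the Wilcoxon rank-sum test, saying beforehand how deaths in the ICU are ranked.
- **Binary endpoints.** Keep chi-square or Fisher's exact. State the sample at which the decrease is judged and the denominator for improvement, and say whether the benefit named under Anticipated Outcome means the improvement rule or the eGFR values themselves.
- **Timing.** Date the change before unblinding. The Abstract says that the study began in May 2021, so if the data are already unblinded, label the analysis post hoc.

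The cost is wording and slightly more analysis work. Both methods are available in SPSS, and the preoperative and four postoperative values are already planned. The drawback is that a contrast averaged over time loses power if the benefit fades by 120 h, and can have less power than the binary decrease if it is confined to a subset. The per-time differences and the retained binary endpoints would show either pattern.

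### The only written definition of eGFR improvement measures a late rise from 48 h without reference to the preoperative value, and no outcome is designated primary

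*Combined protocol and SAP*

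**What the plan says.** The Anticipated Outcome section expects a protective effect "Measured by the improvement of post operative eGFR". The first of three numbered aims is "to Analyze trends in estimated glomerular filtration rate parameters from administration of low-dose furosemide continuous infusion". Evaluation Criteria states that "changes in glomerular filtration rate parameters after intervention in subjects will be evaluated" and adds the need for therapeutic diuretics, then "use of renal replacement therapy, length of stay in the ICU and incidence of mortality will be analyzed". None of these is called primary or secondary.

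The Abstract (Methods) supplies the only operational definitions:

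- Decrease: "A decrease in GFR > 20% of the preoperative value is considered a decrease in renal function". No sampling time is attached.
- Improvement: "an increase of >20% of third sample value in the fourth sample is considered an improvement of renal function". By the stated schedule (12, 24, 48 and 120 h) this runs from 48 h to 120 h.
- Acute renal failure: "Deterioration of renal function to severe renal dysfunction or requiring renal replacement therapy is considered an event of acute renal failure".

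Metode Analisa names chi-square and Fisher's exact test for the comparison of the two groups and gives one threshold: "The level of statistical significance refers to the P value <0.05". It does not rank the outcomes or divide the 5% among them.

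**The concern.** The Abstract's background describes the clinical aim as stopping kidney function from getting worse. A measure of that aim has to look back to the preoperative value. The improvement rule looks back only to 48 h, so it records rebound. Patients who fell furthest by 48 h have the most room to rebound, and a drug that prevents the fall takes that room away. A trial in which furosemide works could then report fewer improvements on furosemide than on control.

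The missing hierarchy makes this worse. eGFR trends, eGFR changes, the decrease, the improvement, acute renal failure, diuretic need, renal replacement therapy (RRT), ICU stay and death all stand side by side under one P value threshold. Two of the renal definitions can point in opposite directions in the same data, and the plan does not say which would carry the conclusion.

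**Working it through.** **Inputs from the documents.** Samples at 12, 24, 48 and 120 h; 43 furosemide and 44 control patients; chi-square or Fisher's exact test; P<0.05 (taken as two-sided; the plan does not say). The plan gives no event rate, SD, effect size or power, so it has no figure of its own to reproduce here.

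**Step 1: single patients, no distributional assumption.** The rule counts a patient if eGFR(120 h)/eGFR(48 h) − 1 > 0.20.

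| Preoperative | 48 h | 120 h | Change 48–120 h | Counted? | 120 h against preoperative |
|---|---|---|---|---|---|
| 60 | 60 | 60 | 0% | no | 0% |
| 60 | 45 | 55 | 55/45 − 1 = +22.2% | yes | 55/60 − 1 = −8.3% |
| 60 | 60 | 73 | 73/60 − 1 = +21.7% | yes | +21.7% |

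The third row shows that an earlier fall is not strictly required.

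**Step 2: the drug prevents part of the fall (trajectories, SDs and correlations are assumptions).** Let m48 and m120 be the median ratios to the preoperative value. Let s be the SD of the log ratio (0.15 or 0.20) and ρ the correlation between times (0.6 or 0.8). Then

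P(improved) = 1 − Φ{[ln 1.2 − ln(m120/m48)] / [s√(2(1 − ρ))]}.

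Control falls 25% at 48 h and is 8% down at 120 h: ln(0.92/0.75) = 0.204. Furosemide halves both: ln(0.96/0.875) = 0.093. The threshold is ln 1.2 = 0.182. The chance of P<0.05 is summed exactly over the two binomials, using uncorrected chi-square, or Fisher if an expected count is below 5.

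| s | ρ | s√(2(1 − ρ)) | Improved, furosemide | Improved, control | P<0.05 favouring control |
|---|---|---|---|---|---|
| 0.15 | 0.6 | 0.134 | 0.252 | 0.565 | 0.857 |
| 0.15 | 0.8 | 0.095 | 0.172 | 0.592 | 0.988 |
| 0.20 | 0.6 | 0.179 | 0.308 | 0.549 | 0.630 |
| 0.20 | 0.8 | 0.126 | 0.239 | 0.569 | 0.893 |

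If exactly one third of the fall remains at 120 h (8.3% and 4.2%), the lowest value in the last column becomes 0.613. With a milder control course (15% down at 48 h, 5% at 120 h, both halved), the rates are 9%–23% against 23%–35%, and control is favoured in 21%–42% of trials.

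**Step 3: no recovery by 120 h.** Here m120/m48 = 1 in both arms, so both have the same rate, 3% to 15%, even if the drug prevents the whole fall. The measure misses the benefit.

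**Step 4: the drug aids recovery after 48 h.** Same formula and ranges:

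- Both arms 25% down at 48 h; at 120 h furosemide 8% down, control 17% down: furosemide favoured in 57%–98% of trials.
- Same, but control does not recover: 98%–100%.
- Furosemide 12.5% down, then 4% down; control 25% down at both times: 40%–62%.

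**Step 5: the plan's own decrease rule in the step 2 scenario.** P(fall >20%) = Φ[(ln 0.8 − ln m)/s].

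- At 48 h: furosemide 28%–33%, control 63%–67%; furosemide favoured at P<0.05 in 82%–97% of trials.
- At 120 h: 11%–18% against 18%–24%; furosemide favoured in only 10%–11%.

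A simulation of the eGFR difference adjusted for preoperative eGFR (preoperative mean 62, SD 15, truncated to 30–89) gives the same contrast: power of 93% or more at 48 h, 17%–26% at 120 h.

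**The case against.** **The wording may be loose.** In the Anticipated Outcome, improvement may mean only better postoperative eGFR than control, and that section does not point to the Abstract's rule. This stands: joining the two is an inference, and a reader should not conclude that the plan has formally chosen the 48 h to 120 h rise as its primary outcome. But no other meaning is given. On the loose reading, no lead measure is defined at all.

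**The plan already has a rule referred to the preoperative value.** This also stands. The decrease of more than 20% is closer to protection, and a reader would be wrong to infer that every renal measure ignores the preoperative value. What it lacks is a time and primary status.

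**The improvement rule can show benefit.** A reader might infer that it can never favour an effective drug. Step 4 shows otherwise. Steps 2 and 3 hold when the drug blunts the early fall and both arms recover the same share of it. The documents do not say which form the benefit would take.

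**Multiplicity.** A reader might attach a particular false-positive rate to the unranked list. Five independent tests would give 1 − 0.95^5 = 22.6%, but these outcomes are related, and the plan does not say that each would support a claim. Any such figure would rest on event rates and tests that the plan does not state, so none is claimed here.

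**Conclusion.** The point holds and should be corrected. As written, the improvement rule measures change after 48 h, and its direction depends on how the drug works. If furosemide prevents the early fall, which matches the aim in the Abstract's background, the rule can miss the benefit or significantly favour control. In the main scenario the reversal occurs in about 61% to 99% of trials, and with the milder fall in about 21% to 42%. These sizes rest wholly on assumed trajectories, SDs and correlations. The single-patient examples need none of them. If furosemide aids late recovery, the rule can favour it.

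Separately, with no primary outcome and one unallocated threshold, the measure that carries the conclusion can be chosen after results are seen. The 5% level would then not describe the error rate of that conclusion. The documents do not show that such a choice was made.

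**What to change.** Before unblinded results are seen, add a dated paragraph that does the following.

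1. Name one primary outcome measured against the preoperative value at one fixed, justified time, using a sample already planned. It can be the decrease of more than 20%, compared by the plan's chi-square or Fisher test, or the between-group eGFR difference adjusted for preoperative eGFR in a linear model, which would have to be added to Metode Analisa.
2. Choose the time with power in mind. Step 5 shows how little remains to detect at 120 h if most of the fall has recovered.
3. Analyse all randomised patients in their allocated arm, and state how death or RRT before that time counts, for example as a decrease or as the worst rank. The documents do not say whether sampling continues after a patient meets a withdrawal criterion. If it does not, a rule for the missing values is needed too.
4. Report the 48 h to 120 h rise as a secondary late change from 48 h, not on its own as evidence of protection. Report the other outcomes as secondary with 95% confidence intervals.

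The change needs no new patients, and no new samples if planned sampling is completed. Its price is that a significant result at another time or on another outcome can no longer carry the main claim. The study began on May 28, 2021 and parts of its conduct are described in the past tense, so results may already have been seen; the documents do not say. If they have, the choice of primary should be labelled post hoc.

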Renal dysfunction is consistently an independent risk factor for the development of cardiovascular disease. Several studies have identified that renal dysfunction increases the risk of mortality in patients undergoing cardiac surgery and that the risk increases with the degree of renal dysfunction. Several strategies are used to prevent worsening of kidney function, such as the use of loop diuretics furosemide as prophylactic. Several recent studies have investigated the protective effect of furosemide in cardiac surgery in preventing worsening of renal function, but these studies mostly were conducted in patients with normal renal function. Patients with preoperative renal dysfunction are more in urgent need of effective renal protective strategies. Based on above, this study aimed to analyze the effect of continuous administration of low-dose furosemide on patients with mild to moderate renal dysfunction undergoing cardiac surgery.

Methods:

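### The >20% improvement rule measures recovery from 48 h to 120 h: protection already present at 48 h earns no credit, and a control arm that catches up late can score better

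*Combined protocol and SAP*

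**What the plan says.** The Abstract (Methods) fixes the sampling times. "After drug administration was completed (12 hours) the first blood sample was obtained", and then "Sampling was repeated again at the 24th hour, 48th hour and 120th hour since the drug was started". The third sample is therefore the 48 h value and the fourth the 120 h value.

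Two classification rules follow, with different references:

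- Decrease: "A decrease in GFR > 20% of the preoperative value is considered a decrease in renal function". No sample time is attached.
- Improvement: "an increase of >20% of third sample value in the fourth sample is considered an improvement of renal function". The preoperative value plays no part.

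Elsewhere, Anticipated Outcome says the protective effect is "Measured by the improvement of post operative eGFR". The first of the Aims is "to Analyze trends in estimated glomerular filtration rate parameters", and Evaluation Criteria says "changes in glomerular filtration rate parameters after intervention in subjects will be evaluated". For comparing the groups, Metode Analisa names only chi-square or Fisher's exact test. No eGFR measure is named as primary.

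**The concern.** The trial's rationale is prevention. The Abstract (Background) says "Several strategies are used to prevent worsening of kidney function, such as the use of loop diuretics furosemide as prophylactic". A preventive effect shows up as eGFR that does not fall, so its natural reference is the preoperative value. The improvement rule uses a postoperative value instead, measured after the randomised infusion has ended. A drug that prevents the early fall leaves its patients little to recover, while an untreated arm that falls and then rebounds collects improvements.

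If the 48-to-120 h rise is read as the improvement that Anticipated Outcome treats as the measure of protection, an effective drug could look no better than saline, or worse. The decrease rule, read at 48 h in the same trial, could favour the drug. Both results would describe one coherent course (less early loss, less to regain), but the label would present one of them as evidence against protection.

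**Working it through.** **1. What the rule tests.** Improved if eGFR(120 h) / eGFR(48 h) > 1.20. The infusion lasts 12 h, so the reference is taken 48 − 12 = 36 h after it ends.

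**2. Direction, with no assumed data.** Suppose furosemide multiplies a patient's 48 h eGFR by *a* and the 120 h eGFR by *b*. The tested ratio is multiplied by *b/a*.

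- *b = a*: every classification is unchanged, so the rule is blind to the benefit.
- *b < a*: improvements can only be lost or stay equal.
- *b > a*: improvements can only be gained or stay equal.

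**3. Illustrative patients** (preoperative / 48 h / 120 h):

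- 60/60/60, fully protected: ratio 1.00, not improved.
- 60/72/72, 20% above preoperative at both times: ratio 1.00, not improved.
- 60/45/60, 25% fall then full return: ratio 1.33, improved.
- 60/40/50, still 17% below preoperative at 120 h: ratio 1.25, improved.

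A patient who returns exactly to the preoperative value by 120 h is improved only if the 48 h value was below 1/1.2 = 83.3% of it, a fall of more than 16.7%.

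**4. Size, under assumptions.** From the documents: 44 control, 43 furosemide, P < 0.05 (two-sided assumed), chi-square. Assumed, because the documents give none: mean eGFR as a percentage of preoperative at 48 h/120 h, SD 15 points, correlation 0.6, all randomised patients in the denominator, and no continuity correction. In a normal model, with *m* and SD as fractions of preoperative,

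P(improved) = Φ((m120 − 1.2·m48) / (SD·√(2.44 − 2.4ρ))).

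At SD 0.15 and ρ = 0.6 the divisor is 0.15 × √1.00 = 0.15. Example, middle pattern: control (0.90 − 1.2 × 0.75)/0.15 = 0, giving 50%; furosemide (0.95 − 1.2 × 0.85)/0.15 = −0.467, giving 32%. Exact binomial enumeration over 44 and 43 then gives the chance of a significant result:

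| Pattern (control vs furosemide) | b/a of means | Improved, control vs furosemide | Significant for control | Significant for furosemide |
|---|---|---|---|---|
| Small catch-up (85/95 vs 90/97) | 0.964 | 32% vs 23% | 15.4% | 0.2% |
| Middle catch-up (75/90 vs 85/95) | 0.931 | 50% vs 32% | 40.0% | 0.0% |
| Large catch-up (70/90 vs 85/95) | 0.869 | 66% vs 32% | 89.6% | 0.0% |
| Constant 10 points (75/80 vs 85/90) | 0.993 | 25% vs 21% | 6.6% | 0.8% |
| Benefit only after 48 h (75/80 vs 75/92) | 1.15 | 25% vs 55% | 0.0% | 83.2% |

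**5. Sensitivity.**

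- SD 10 to 20 points and correlation 0.4 to 0.8: significant for control in 9–33%, 19–93% and 52–100% (small, middle, large) and 5–9% (constant); significant for furosemide in 45–100% (late).
- Continuity-corrected chi-square: 9.8%, 31.4% and 85.0% for control; 77.0% for furosemide (late).
- Log-normal model (log SD 0.18, correlation 0.6): 12.5%, 36.6% and 89.9% for control; constant 3.6% for control and 1.7% for furosemide; late 88.4% for furosemide. With a benefit of exactly constant proportion (80/90 vs 93.3/105), 34.4% improve in each arm.

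**6. Conflict with the decrease rule.** In simulation, the improvement rule is significant for control and the 48 h decrease rule is significant for furosemide in the same trial in about 7%, 33% and 86% (small, middle, large).

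**The case against.** The strongest reply is that the plan never says this rule defines the improvement in Anticipated Outcome. The Aims and Evaluation Criteria speak more broadly of trends and changes. The Abstract may simply be describing a course (worsening, recovery, failure), in which case measuring recovery from a postoperative value is ordinary. Protection has its own preoperative-referenced rule, which on the figures above would detect the middle, large and constant benefits at 48 h with 70%, 96% and 70% power.

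Much of this stands. The link to Anticipated Outcome is an inference, the rule is not named as primary, and the plan as a whole is not blind to early benefit. But no other numeric definition of improvement exists, and the decrease rule has no time point, so nothing prevents the reading described here.

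A second reply concerns the denominator, which the documents do not state. If improvement were counted only among patients more than 20% below preoperative at 48 h, the chance of significance for control falls to about 5%, 9% and 30% (small, middle, large). In the constant pattern the direction turns: about 36% of control and 41% of furosemide patients recover, significant for furosemide in about 5–6% and for control in about 1%. So the sizes do depend on this choice. The rule contains no such restriction, however, and it would compare subgroups selected after randomisation.

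Third, reversal is not inevitable. It needs a control arm that falls by 48 h and regains ground by 120 h, and the rule performs well when the benefit is late.

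**Conclusion.** The concern holds. As written, the rule measures change between 48 h and 120 h and cannot credit protection already present at 48 h. Confidence in that is high, since it follows from the sampling times and the ratio. Confidence in the sizes is low: the spread from about 15% to 90% in favour of control rests on assumed trajectories, SD and correlation, and on counting all randomised patients. The rule is a legitimate description of recovery; the fault lies in calling it improvement in a trial whose claimed effect is protection. It should be corrected before the results are read.

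**What to change.** - Rename the rule as recovery from 48 h to 120 h, report it descriptively by arm, and do not use it as evidence of protection.
- Judge protection by eGFR change from the preoperative value at one named time point, 48 h or 120 h, compared between arms with adjustment for preoperative eGFR.
- Read the existing >20% decrease rule at that same time point as the supporting binary outcome, with the planned chi-square or Fisher's exact test. Report the other time point as secondary.

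The choice of time point is a real trade-off. Power for furosemide under the same assumptions (for the adjusted comparison, preoperative eGFR is also assumed uniform over 30–89; 8,000 simulated trials):

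| Pattern | Adjusted change, 48 h / 120 h | Decrease rule, 48 h / 120 h |
|---|---|---|
| Small catch-up | 32% / 9% | 22% / 6% |
| Middle catch-up | 83% / 31% | 70% / 19% |
| Large catch-up | 99% / 32% | 96% / 19% |
| Constant benefit | 84% / 84% | 70% / 67% |
| Late benefit | 3% / 94% | 3% / 82% |

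Neither time point is best in every pattern, so it must be fixed before unblinding.

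The cost is one reworded sentence in the Abstract, a time point added to the decrease rule, and one baseline-adjusted comparison added to Metode Analisa, which names no test for continuous eGFR. The preoperative, 48 h and 120 h values are already planned. Because the study started on 28 May 2021, the change should be dated and recorded as made after study start and before unblinding. If unblinding has already happened, the comparison should be labelled post hoc.
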